6.8.4 Pituitary Dysfunction

Based on the expression of DLL3 in the pituitary and observations in the cynomolgus monkey toxicology study, there is a key risk of pituitary dysfunction in humans with administration of tarlatamab.

Early recognition of signs and symptoms and prompt intervention are essential. Symptoms may derive from hormonal deficiencies and by the mass effect due to the swelling of the gland. The most common presentation includes headaches, asthenia, fatigue, nausea, weakness, lethargy, erectile dysfunction, and loss of libido.

The diagnosis and management of pituitary gland dysfunction should be performed according to the guidelines provided in **Table 6-7**. Adrenocorticotropic hormone (ACTH), cortisol, TSH, free thyroxine (FT4) will be evaluated at screening and monitored throughout the study. Prolactin and follicle stimulating hormone (FSH)/luteinizing hormone (LH), testosterone (in males) and estradiol (in females) will also be evaluated at screening, end of therapy and as clinically indicated. After a confirmed diagnosis, tarlatamab will be withheld, and corticosteroids and hormone replacement administered if clinically indicated. Please see Section 6.2.2.1.3 for guidelines for restarting tarlatamab. This management recommendation may be revised based on emerging clinical data.

Protocol Number: 20200439

Date: 05 June 2024 Page 82 of 176

Table 6-7 Monitoring and Management of Pituitary Gland Dysfunction (González-Rodríguez and Rodríguez-Abreu, 2016; Brahmer et al, 2018)

- Monitor for signs and symptoms of pituitary gland dysfunction, TSH, FT4, cortisol, and ACTH throughout study (prolactin, FSH, LH, testosterone [in males] and estradiol [in females] will be evaluated only at screening, EOT, and as clinically indicated)
 - Abnormal hormone monitoring result or clinical suspicion of pituitary gland dysfunction (headache, fatigue, asthenia, impaired vision, vomiting, hypotension, amenorrhea, impotence)
 - Diagnostic tests: consider brain MRI (if clinically indicated) with or without contrast with pituitary/sellar cuts in subjects with multiple endocrine abnormalities and/or with new headache or vision changes. Evaluate ACTH, AM Cortisol, TSH, FT4, electrolytes and consider evaluating LH, FSH, and testosterone levels in males or estrogen females.
- Obtain endocrinology consultation for hypophysitis or if clinically indicated
- Once pituitary gland dysfunction is confirmed, hold further treatment with tarlatamab pending completion of evaluation. Manage pituitary dysfunction according
 to NCCN or ASCO guidelines for Management of Immune-Related Adverse Events in Patients Treated with Immune Checkpoint Inhibitor Therapy (NCCN
 Guidelines, 2021; Brahmer et al, 2018).
- Once stabilized on any replacement hormones and taking mg or less of prednisone or equivalent may consider restarting tarlatamab. If subject experienced grade 3 or higher pituitary dysfunction, must discuss with medical monitor prior to restarting treatment.
- Continue endocrinological surveillance

ACTH = adrenocorticotropic hormone; **ASCO = American Society of Clinical Oncology;** EOT = end of treatment; FSH = follicle stimulating hormone; FT4 = free thyroxine; LH = luteinizing hormone; MRI = magnetic resonance imaging; **NCCN = National Comprehensive Cancer Network;** TSH = thyroid stimulating hormone

Protocol Number: 20200439

Date: 05 June 2024 Page 83 of 176

6.8.5 Neutropenia

Neutropenia has been observed in patients receiving tarlatamab. The risk mitigation plan includes monitoring of laboratory parameters (including, but not limited, to white blood cell [WBC] count and absolute neutrophil count) which will be evaluated at baseline and monitored throughout the study. Specific recommendations for the management of neutropenia, and infusion interruption and stopping rules are found in the **Table 6-8**.

Protocol Number: 20200439

Date: 05 June 2024 Page 84 of 176

Table 6-8. Tarlatamab Dose Modification Guidelines for Neutropenia

Grade	Interruption/ Delay	Specific Management	Re-start guidance	Permanent Discontinuation			
Non-febrile	Non-febrile Neutropenia						
3	Interrupt tarlatamab until the event improves to grade ≤ 2	Assess for other potential etiologies of neutropenia, including concomitant medications and underlying infection Consider bone marrow biopsy, anti-neutrophil antibodies Granulocyte colony-stimulating factor (G-CSF)	Resume tarlatamab no less than 72 hours after the initial observation of the grade 3 adverse event at the same dose level	Initial grade 3 non-febrile neutropenia does not improve to ≤ grade 2 in 3 weeks			
4	Interrupt tarlatamab until the	Assess for other potential etiologies of	Resume tarlatamab no less than	Initial grade 4 non-febrile			
	event improves to grade ≤ 2	neutropenia, including concomitant medications and underlying infection	72 hours after the initial observation of the grade 4	neutropenia event that lasts > 7 days			
		Consider bone marrow biopsy, anti-neutrophil antibodies	adverse event and discuss with medical monitor the restarting				
		Consider G-CSF administration	dose				

G-CSF = granulocyte colony-stimulating factor

Protocol Number: 20200439

Date: 05 June 2024 Page 85 of 176

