6.2.2.1.2 Dose Delays

During the first DLT observation period, if the dosing of tarlatamab is delayed for more than 72 hours for reasons other than DLT during the DLT evaluation period, a replacement subject may be enrolled and assigned to the same dose level. The subject may continue on study only after discussion with the Medical Monitor.

After the DLT observation period, if the dosing of tarlatamab is delayed for ≤ 2 weeks, the subject should resume the treatment as soon as possible if deemed safe by the investigator. If the dosing of tarlatamab is delayed between 2 to 4 weeks due to severe or life-threatening treatment-related adverse events, the subject can resume treatment if the toxicities resolve to grade ≤ 1 or return to subjects' baseline values within 3 weeks and restarting of therapy has been deemed safe by the investigator and medical monitor.

If the dosing of tarlatamab is delayed for more than 4 weeks due to severe or life-threatening treatment-related adverse events, the subject will be discontinued from investigational product. If the dosing delay occurred under other conditions, the case will be reviewed by the sponsor to determine whether and when the subject will be allowed to resume tarlatamab.

Protocol Number: 20200439

Date: 05 June 2024 Page 61 of 176

For adverse events related to CRS, neurological events, and pituitary dysfunction, please see Sections 6.8.1, 6.8.3, and 6.8.4 respectively for guidelines for dose delays.

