6.2.2.1.3 Rules for Withholding or Restarting

Tarlatamab should be withheld for any of the following:

- DLT
- Symptomatic hypophysitis (See Section 6.8.4)
- Criteria for conditional withholding of tarlatamab due to potential hepatotoxicity (Section 11.7)

Tarlatamab dosing can be resumed if the toxicities resolve to grade \leq 1 or return to subjects' baseline values within 3 weeks. The restarting of therapy should be deemed safe by the investigator and medical monitor.

Subjects should not be restarted with tarlatamab if the following treatment-related adverse events occur:

- Criteria for permanent withholding of tarlatamab due to potential hepatotoxicity (Section 11.7)
- Any grade ≥ 4 adverse events except those not considered DLT as described in Section 6.2.1.4
- Grade 3 adverse event(s) that do not recover to grade ≤ 1 within 3 weeks
- Any grade 3 adverse events that recur (with the exception of grade 3 laboratory parameters not considered clinically relevant or recurrent non-febrile grade 3 neutropenia which resolves with supportive care to grade ≤ 1 or returns to subjects' baseline values within 3 weeks)

For adverse events related to CRS, neurological events and pituitary dysfunction, please see Sections 6.8.1, 6.8.3, and 6.8.4 respectively for guidelines for dose adjustment.

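### For a first, treatment-related grade 3 non-febrile neutropenia that improves only to grade 2, Protocol Table 6-8 and Sections 6.2.2.1.1 and 6.2.2.1.3 give opposite restart instructions, and no text says which governs

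*Protocol*

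**What the plan says.** Protocol Section 6.8.5, Table 6-8, grade 3 non-febrile row:

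- Interruption: "Interrupt tarlatamab until the event improves to grade ≤ 2".
- Restart: "Resume tarlatamab no less than 72 hours after the initial observation of the grade 3 adverse event at the same dose level".
- Permanent discontinuation: "Initial grade 3 non-febrile neutropenia does not improve to ≤ grade 2 in 3 weeks".

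Protocol Section 6.2.2.1.3 opens its no-restart list with "Subjects should not be restarted with tarlatamab if the following treatment-related adverse events occur". One item is "Grade 3 adverse event(s) that do not recover to grade ≤ 1 within 3 weeks". The next item covers grade 3 events that recur, and exempts "recurrent non-febrile grade 3 neutropenia which resolves with supportive care to grade ≤ 1" or to baseline within 3 weeks. The section then sends certain events elsewhere: "For adverse events related to CRS, neurological events and pituitary dysfunction, please see Sections 6.8.1, 6.8.3, and 6.8.4 respectively". Neutropenia and Section 6.8.5 are not in that list.

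Protocol Section 6.2.2.1.1 allows resumption after an adverse event once it is at grade 0 to 1. Protocol Section 6.2.2.1.2, for delays of 2 to 4 weeks caused by severe or life-threatening related events, says "the subject can resume treatment if the toxicities resolve to grade ≤ 1" or return to baseline within 3 weeks. Both sections close with the same three event-specific cross-references, again without Section 6.8.5.

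**The concern.** Neutropenia is an identified risk of tarlatamab (Protocol Section 2.3.3.1), so sites will have to use these rules. A site working from Table 6-8 restarts a subject at grade 2. A site working from the general dose-modification sections waits for grade 1 and, if that is not reached in 3 weeks, does not restart. Each site can point to current protocol text.

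The first stake is how the subject is managed. The second is how the safety summaries read. SAP Section 9.6.2 lists neutropenia as an event of interest and summarises such events leading to interruption, reduction or discontinuation. SAP Section 9.6.8 summarises relative dose intensity and dose modifications with their reasons. If sites follow different passages, part of what those tables show is which passage was followed.

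**Working it through.** No plan figure has to be reproduced and no arithmetic applies. The check takes one case, a first, treatment-related, non-febrile grade 3 neutropenia, and reads each rule at every possible level of recovery.

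| Best recovery | Table 6-8 | Section 6.2.2.1.1 | Section 6.2.2.1.3, recovery bullet |
|---|---|---|---|
| Grade 0 to 1 within 3 weeks | Resume, same dose level | Resumption allowed | No bar |
| Grade 2, before 3 weeks have passed | Resume once 72 hours have passed since first observation | Not yet allowed | Not yet triggered |
| Grade 2 at 3 weeks | Discontinuation criterion not met; resumption allowed | Not allowed | Do not restart |
| Grade 3 or worse at 3 weeks | Discontinue permanently | Not allowed | Do not restart |

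The first and last rows agree. The two grade 2 rows do not. Before 3 weeks, the conflict is between Table 6-8 and Section 6.2.2.1.1. At 3 weeks, Section 6.2.2.1.3 adds a bar on restart for a subject whom Table 6-8 may already have put back on drug.

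Four further checks:

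1. **Baseline alternative.** The general resumption sentence in Section 6.2.2.1.3 accepts return to baseline. The no-restart bullet does not, so the conflict remains.
2. **Strength of wording.** Section 6.2.2.1.3 says not to restart, while Table 6-8 speaks of permanent discontinuation. For the subject the effect is the same.
3. **Link to DLTs.** Section 6.2.1.4 exempts grade 3 non-febrile neutropenia from being a DLT if it reaches grade 1 or lower within 3 weeks. An event in the DLT window that reaches only grade 2 misses that exemption. Unless another applies, such as an abnormality judged not clinically relevant, it is a DLT. Section 6.2.2.1.3 then withholds tarlatamab until grade 1 or baseline, which again differs from Table 6-8.
4. **Grade 4 comparison.** Section 6.2.1.4 exempts grade 4 non-febrile neutropenia lasting up to 7 days, Section 6.2.2.1.3 carries that exemption into its no-restart list, and Table 6-8 discontinues beyond 7 days. The grade 4 discontinuation criterion was aligned across sections; the grade 3 one was not.

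**The case against.** The best defence is that the specific table overrides the general rule. It has support. Section 6.8.5 and Table 2-1 both name Table 6-8 as the place for the neutropenia interruption and stopping rules. Section 6.2.2.1.1 refers to Section 6.8 as a whole for dose reductions on restart. The discontinuation cell in Table 6-8 is limited to the initial event, and the only item in Section 6.2.2.1.3 that names neutropenia concerns recurrence, so the table could govern first events and the section recurrences.

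Much of this stands. A reader might infer that nothing points a site to Table 6-8, and that is not so. But the defence does not close the gap. No sentence gives the table precedence. The general reference to Section 6.8 concerns dose reductions and is followed at once by the grade 0 to 1 condition. The generic grade 3 bullet has no neutropenia exception, although the next bullet has one. Section 6.2.1.4 cites Section 6.8.5 twice, so the protocol names that section where it wants it applied.

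A second defence is that restart needs agreement from the investigator and medical monitor (Section 6.2.2.1.3), and also the Global Safety Officer (Section 6.2.2.1.1). That does limit divergence between sites. However, the condition sits in the general sections; the grade 3 row of Table 6-8 does not repeat it.

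A third is that no hypothesis is tested and the safety and exposure summaries are descriptive. This also stands: the documents show no effect on any result.

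**Conclusion.** The contradiction is real and narrow. It needs an event that is treatment-related, non-febrile, grade 3, a first occurrence, and improved only to grade 2. A reader might infer that the protocol's grade 3 neutropenia rules conflict throughout. They do not: they agree at grade 0 to 1, and at grade 3 or worse at 3 weeks.

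The number of subjects affected cannot be estimated from the documents. It is tempting to start from the 11.8% with grade 3 or higher neutropenia in Part A2 of the first-in-human study (Protocol Section 2.2.2.3). That rate comes from monotherapy in another study, includes grade 4, and is not restricted to non-febrile, related or first events. Nothing gives the share still at grade 2 after 3 weeks, so any multiplier would be invented.

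Scope for action is limited. Enrollment ended in January 2023 (Protocol Section 4.1) and the current version is dated June 2024. A correction cannot alter past restart decisions and helps only subjects still receiving tarlatamab, for whom the protocol keeps a monotherapy schedule (Table 1-2). It is still worth making, because it removes opposite restart instructions for an identified risk. The conclusion rests on the text of the passages alone.

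**What to change.** Reconcile Section 6.2.2.1.1, Section 6.2.2.1.3 and Table 6-8 so that one recovery condition applies to a first grade 3 non-febrile neutropenia. Add Section 6.8.5 to the event-specific cross-references that close Sections 6.2.2.1.1 to 6.2.2.1.3, and state which passage governs if they differ. Check the result against the DLT exemption in Section 6.2.1.4 and the delay rule in Section 6.2.2.1.2. Which threshold applies is for the sponsor to decide; this review takes no view.

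The cost is wording in an amendment or a clarification letter to sites. No design or analysis method changes.

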6.8.6 Tumor Lysis Syndrome

Tumor lysis syndrome, a preventable complication of cancer therapies, is a result of rapid tumor necrosis with release of intracellular ions into the bloodstream. It is characterized by hyperuricemia, hyperkalemia, and hyperphosphatemia. Tumor lysis syndrome occurs primarily in hematological malignancies and high-grade lymphomas. The occurrence of TLS in solid tumors is rare but is more common in highly responsive tumors with large tumor burdens. Pretreatment elevation of serum lactate dehydrogenase (LDH) and uric acid, and pre-existing renal failure are risk factors for the development of TLS (Kallab and Jillella, 2001). In light of the extremely low incidence of TLS in patients with solid tumors, routine prophylactic measures, such as allopurinol and alkaline hydration, cannot be recommended in all patients. However, the potential for TLS in patients with bulky, SCLC who present with renal insufficiency, dehydration, hyperuricemia, and elevated serum LDH levels must be recognized, to allow for appropriate monitoring after treatment and early initiation of therapeutic measures if necessary (Kalemkerian et al, 1997). Intravenous hydration and careful monitoring of fluid status is recommended. Allopurinol or rasburicase can be considered for both prophylaxis and/or treatment of hyperuricemia.

6.8.7 Vaccines

Every effort should be made to fully vaccinate patients prior to days from first dose of tarlatamab. The use of vaccines except live and live-attenuated vaccines will be allowed during therapy per regional and institutional standard of care. However, SARS-CoV-2 vaccinations should be avoided during screening (within a minimum of days from first dose of tarlatamab) and should be also avoided in the first treatment cycle for better assessment of safety parameters. Throughout the trial, SARS-CoV-2 vaccination should be avoided within days after the administration of tarlatamab. In the event where a patient requires steroids for treatment of adverse events, vaccination should be avoided while on steroids.

6.8.8 Management of SARS-CoV-2 Infection and COVID-19 Disease

Management of SARS-CoV-2 infection and COVID-19 should be performed according to the guidelines provided in **Table 6-9** (exceptions may be permitted with medical monitor approval).

Protocol Number: 20200439

Date: 05 June 2024 Page 86 of 176

Table 6-9. Infusion Interruptions/Delays/Withholding/Permanent Discontinuation and Management of SARS-CoV-2 Infection and COVID-19 Disease

Grade	Interruption/ Delay	Specific Management	Re-start guidance	Permanent Discontinuation
SARS-Co	V-2 infection and COVID-19 o	lisease		
Asympto matic	Interruption required until at least 10 days since positive SARS-CoV-2 test UNLESS patient previously fully vaccinated against SARS-CoV-2. If patient previously vaccinated and tests positive, then discuss with medical monitor.	Follow local guidelines and standard of care for COVID-19 treatment and isolation Contact Amgen Medical Monitor within 1 business day to ensure appropriate documentation and management of study activities	 Re-start possible upon agreement between investigator and Amgen Medical Monitor provided: There are no new findings on physical exam related to SARS-CoV-2, AND Subject tests negative for SARS-CoV-2 by RT-PCR Consider CT of the chest imaging, ECG, ECHO, and cardiology assessment prior to re-start of investigational product. OR If subject continues to test positive for SARS-CoV-2 more than 10 days after initial positive test, or if subject initially tests positive in the setting of prior COVID vaccination, resume investigational product only after discussion with patient and reassessment of individual risk/benefit and perform CT of chest imaging and ECG required prior to re-start of investigational product. Consider ECHO and cardiology assessment Consider hospitalization for re-start of investigational product based on length of treatment interruption, risk of CRS at restart, and amount of time since patient was last treated Dose modification: resume at the same dose or reduce to next lower dose if clinically indicated Premedication and assessments: follow guidance in SOA tables 	Immediately stop the infusion (if applicable) and permanently discontinue investigational product therapy if: Subject required treatment interruption greater than 28 days and upon discussion with Amgen medical monitor the decision is made to permanently discontinue treatment OR Initial benefit/risk assessment for individual patient is no longer favorable

Footnotes defined on last page of this table.

Protocol Number: 20200439

Date: 05 June 2024 Page 87 of 176

Table 6-9. Infusion Interruptions/Delays/Withholding/Permanent Discontinuation and Management of SARS-CoV-2 Infection and COVID-19 Disease

Grade	Interruption/ Delay	Specific Management	Re-start guidance	Permanent Discontinuation
SARS-Co\	/-2 infection and COVID	-19 disease		
Symptom atic	Interruption required until at least 10 days since complete resolution of acute symptoms	Follow local guidelines and standard of care for COVID-19 treatment and isolation Contact Amgen Medical Monitor within 1 business day to ensure appropriate documentation and management of study activities	Re-start possible upon agreement between investigator and Amgen medical monitor provided: There are no new findings on physical exam and chest imaging, related to SARS-CoV-2 Subject tests negative for SARS-CoV-2 by RT-PCR Consider CT of the chest imaging and ECG, ECHO and cardiology assessment prior to re-start of investigational product. OR If subject continues to test positive for SARS-CoV-2 more than 10 days after initial positive test, resume investigational product only after discussion with patient and reassessment of individual risk/benefit and perform CT of chest imaging and ECG required prior to re-start of investigational product. Consider ECHO and cardiology assessment Consider hospitalization for re-start of investigational product based on length of treatment interruption, risk of CRS at restart, and amount of time since patient was last treated Dose modification: resume at the same dose or reduce to next lower dose if clinically indicated Premedication and assessments: follow guidance in SOA tables	Immediately stop the infusion (if applicable) and permanently discontinue investigational product therapy, if: Subject required treatment interruption greater than 28 days due to severe or life-threatening COVID-19 OR Initial benefit/risk assessment for individual patient is no longer favorable

Page 2 of 2

COVID-19 = coronavirus disease 2019; CRS = cytokine release syndrome; CT = computed tomography; ECG = electrocardiogram; ECHO = echocardiogram; RT PCR = real time polymerase chain reaction; SARS-CoV-2 = severe acute respiratory syndrome coronavirus 2; SOA = Schedule of Activities

Protocol Number: 20200439

Date: 05 June 2024 Page 88 of 176

7. Discontinuation of Study Treatment and Subject Discontinuation/Withdrawal

Subjects have the right to withdraw from investigational product and/or other protocol-required therapies, protocol procedures, or the study as a whole at any time and for any reason without prejudice to their future medical care by the physician or at the institution.

The investigator and/or sponsor can decide to withdraw a subject(s) from investigational product, device, and/or other protocol-required therapies, protocol procedures, or the study as a whole at any time prior to study completion for the reasons listed in Section 1.

7.1 Discontinuation of Study Treatment

Subjects (or a legally acceptable representative) can decline to continue receiving investigational product and/or other protocol-required therapies and/or procedures at any time during the study but continue participation in the study. If this occurs, the investigator is to discuss with the subject the appropriate processes for discontinuation from investigational product or other protocol-required therapies and must discuss with the subject the possibilities for continuation of the Schedule of Activities (see Section 1.3) including different options of follow-up (eg, in person, by phone/mail, through family/friends, in correspondence/communication with other treating physicians, from the review of medical records) and collection of data, including endpoints, adverse events, and must document this decision in the subject's medical records. Subjects who have discontinued investigational product, and/or other protocol-required therapies and/or procedures should not be automatically removed from the study. Whenever safe and feasible, it is imperative that subjects remain on-study to ensure safety surveillance and/or collection of outcome data.

Reasons for early removal from protocol-required investigational product(s) or procedural assessments may include any of the following:

- Decision by sponsor
- Lost to follow-up
- Death
- Adverse event
- Subject request
- Ineligibility determined
- Protocol deviation
- Non-compliance

Protocol Number: 20200439

Date: 05 June 2024 Page 89 of 176

 Confirmed disease progression as defined by modified RECIST 1.1 criteria (Section 11.9) or disease progression accompanied by worsening of symptoms or deterioration of the subject's general condition

*Note: Subjects with confirmed disease progression per modified RECIST 1.1 criteria who have clinical benefit in the investigator's judgment may be allowed to continue treatment after approval by the Medical Monitor as per Section 7.2

- Requirement for alternative therapy
- Protocol-specified criteria:
 Subjects who require more than 1 dose reduction

